## 1 PROTOCOL SUMMARY

### 1.1 Synopsis

**Protocol Title:** A Phase IIa, Randomized, Double-blind, Placebo-controlled Study to Evaluate the Safety, Tolerability, and Pharmacodynamics of AZD4831 (mitiperstat) in Participants with Non-cirrhotic Non-alcoholic Steatohepatitis (NASH) with Fibrosis (COSMOS)

**Short Title:** A Phase IIa Study to Assess Safety, Tolerability, and Pharmacodynamics of AZD4831 (mitiperstat) in Adult Participants with Non-cirrhotic NASH with Fibrosis (COSMOS)

**Rationale:** The primary objective of this study is to evaluate safety and tolerability of AZD4831 (mitiperstat) and pharmacodynamics in participants with non-cirrhotic NASH with fibrosis.

### Objectives and Endpoints

Objectives	Endpoints
Primary	
To assess the effect of AZD4831 (mitiperstat) on circulating markers of hepatic injury and apoptosis or necrosis compared with placebo	Change from baseline and over placebo to Week 12: 

ALT

Secondary	
To assess the effect of AZD4831 (mitiperstat) on circulating biomarkers of fibrosis compared with placebo	Change from baseline and over placebo to Week 12: 

Pro-C3

To assess the PK of AZD4831 (mitiperstat)	Plasma concentration of AZD4831 (mitiperstat) will be summarized by timepoints. If PK data permit, a population PK model may be developed and potentially coupled with separate PD models; the derived PK parameters and the modeling may be provided in a separate PK and population PK/PD report.
Safety	
To assess safety and tolerability of AZD4831 (mitiperstat) compared with placebo in participants with non-cirrhotic NASH with fibrosis	Safety and tolerability, including hepatic safety, will be evaluated in terms of AEs (including AESIs related to skin reactions, including maculopapular rash, and infection) and clinical and laboratory assessments.

AE, adverse event; AESI, adverse event of special interest; ALT, alanine aminotransferase; NASH, non-alcoholic steatohepatitis; PD, pharmacodynamic(s); PK, pharmacokinetic(s); Pro-C3, released N-terminal propeptide of type III collagen

Exploratory objectives and endpoints are provided in Section 3.

## Overall Design

This is a randomized, double-blind, placebo-controlled, parallel-group, multicenter study including a maximum of approximately 90 randomized adult participants with biopsy-proven non-cirrhotic non-alcoholic steatohepatitis (NASH) with fibrosis (NAS  $\geq$  4, fibrosis stages F1, F2, F3). The study will be conducted at approximately 48 sites across approximately 9 countries.

During screening, the participants will be checked for eligibility and enrolled in the study. Following an 8-week screening period, approximately 90 participants will be randomized at Visit 4 in a 1:1 ratio to once daily dosing of 5 mg AZD4831 (mitiperstat) or placebo. Participants, including participants who are rescreened, can be randomized anytime within the screening period outlined in the SoA ([Table 2](#)) once all inclusion/exclusion criteria have been fulfilled. For participants who have a historical biopsy and elevated alanine aminotransferase (ALT), the screening period can be shortened.

All participants will be treated once daily with 5 mg AZD4831 (mitiperstat) or placebo for 12 weeks. The safety, tolerability, and pharmacodynamics will be evaluated at 12 weeks.

This is the first clinical study to test AZD4831 (mitiperstat) in participants with non-cirrhotic NASH with fibrosis.

**Disclosure Statement:** This is a parallel group treatment study with 2 arms that is participant and investigator blinded.

### Number of Participants:

Approximately 300 participants will be screened/enrolled to achieve approximately 90 participants randomly assigned to study intervention or placebo.

**Note:** “Enrolled” means a participant’s, or their legally acceptable representative’s, agreement to participate in a clinical study following completion of the informed consent process.

Potential participants who are screened for the purpose of determining eligibility for the study, but are not randomly assigned/assigned in the study, are considered “screen failures”, unless otherwise specified by the protocol.

### Intervention Groups and Duration:

Participants will be randomized to once daily dosing of 5 mg AZD4831 (mitiperstat) or placebo. Dosing should be supervised and documented by study staff when study intervention is administered in the clinic.

The study will comprise 3 periods totaling approximately 24 weeks:

- A screening period of up to 8 weeks

- A total treatment period of 12 weeks
- A safety follow-up period of 4 weeks

**Data Review Committee:** An unblinded safety data review committee consisting of AstraZeneca personnel and an external dermatologist will be set up for ongoing, periodic safety monitoring, with a focus on skin reactions and study stopping criteria.

### Statistical Methods

The primary pharmacodynamic endpoint of this study is change from baseline to Week 12 in alanine aminotransferase (ALT), and it will be assessed through a treatment policy estimand. This approach will assess the effect of the treatment policy of AZD4831 (mitiperstat) and placebo regardless of discontinuation of study medication. The main analysis will be using a mixed effects linear model with participant as random effect, treatment, visit, and treatment-by-visit interaction as fixed effects, and baseline as covariate, including all participants in the full analysis set (FAS). Data will be log-transformed before analyses, and results will be back-transformed to describe relative change versus placebo in value at end of treatment relative to baseline.

The null hypothesis of no decrease in ALT comparing AZD4831 (mitiperstat) to placebo will be tested versus the alternative hypothesis of a decrease in ALT in favor of AZD4831 (mitiperstat) to placebo using a one-sided test at 5% significance level.

The secondary endpoint Pro-C3 will be analyzed in the same way as ALT.

The study has been powered to have at least 80% power to detect a 25% decrease in ALT level at end of treatment relative to baseline for AZD4831 (mitiperstat) treated versus placebo treated in a one-sided test at 5% significance level, based on the FAS population. ALT measurements will be log-transformed before analysis. Under the assumption of a standard deviation of 0.50 for change from baseline in log-transformed ALT, and allowing for 10% missing data, 45 participants per arm would render the desired power.

[figure not shown]
Safety analyses will be performed using the safety analysis set, which includes all participants who receive at least 1 dose of randomized AZD4831 (mitiperstat) or placebo. Safety data will be presented using descriptive statistics unless otherwise specified and will not be formally tested.

No multiplicity adjustment for alpha is planned.

All personnel involved with the conduct of the study will remain blinded until database lock at 12 weeks and protocol violations have been identified and documented. Analyses will be performed by AstraZeneca or its representatives.

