### **6.3 Measures to Minimize Bias: Randomization and Blinding**

All participants will be blinded with respect to active or placebo treatment.

All participants will be centrally assigned to randomized study intervention using an IRT/RTSM. This computerized randomization procedure will ascertain allocation concealment and will assign the participants 1:1 to AZD4831 (mitiperstat) (5 mg) or placebo. The randomization codes will be computer generated and loaded into the IRT/RTSM database. Before the study is initiated, the log-in information and directions for the IRT/RTSM will be provided to each site.

The study will be blinded to both participants and investigators/site staff as well as to the sponsor (designated sponsor personnel will be unblinded as part of the DRC as described in Section 9.6). The IRT/RTSM will provide to the investigator(s) the kit identification number to be allocated to the participant at the dispensation visit. Study intervention will be dispensed at the study visits summarized in [Table 2](#). Routines for this will be described in the IRT/RTSM user manual that will be provided to each center.

The randomization code should not be broken except in medical emergencies when the appropriate management of the participant requires knowledge of the treatment randomization. The investigator documents and reports the action to AstraZeneca, without revealing the treatment given to the participant to the AstraZeneca staff.

AstraZeneca retains the right to break the code for SAEs that are unexpected and are suspected to be causally related to an IP and that potentially require expedited reporting to regulatory authorities. Randomization codes will not be broken for the planned analyses of data until all decisions on the evaluability of the data from each individual participant have been made and documented.

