#### **8.3.1 Time Period and Frequency for Collecting Adverse Event and Serious Adverse Event Information**

Adverse events will be collected from time of first dose throughout the treatment period and including the follow-up period. The only exception is related to the predose orthostatic test at

Visit 4: If orthostatic hypotension is confirmed, it should be reported as an AE, and symptoms related to the measurement of orthostatic vitals if present should also be reported as an AE.

Serious adverse events will be recorded from the time of signing of the informed consent form.

If the investigator becomes aware of an SAE with a suspected causal relationship to the investigational medicinal product that occurs after the end of the clinical study in a participant treated by him or her, the investigator shall, without undue delay, report the SAE to the sponsor.

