#### **9.4.1 General Considerations**

All personnel involved with the analysis of the study will remain blinded until database lock and protocol violations have been identified and documented. Analyses will be performed by AstraZeneca or its representatives.

Nominal significance will be 5% and all tests will be one-sided. All confidence intervals will be 2-sided and 95%.

No multiplicity adjustment for alpha is planned.

For analyses both on the FAS and on the SAS, baseline is defined as the last non-missing value prior to first dose including unscheduled assessments that occurs prior to first dose.

All summary statistics will be presented in total, divided by fibrosis stage, and divided by T2DM status.

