3 DATA ANALYSIS CONSIDERATIONS

3.1 Timing of Analyses

The study is divided into a screening period of up to 8 weeks, a planned treatment period of 12 weeks followed by a safety follow-up period of 4 weeks.

The final clinical lock for writing the CSR will occur once all subjects have completed their full study participation or withdrawn from study.

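### The synopsis keeps conduct staff blinded only to a 12-week database lock, which conflicts with the SAP's single lock after follow-up to Week 16

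*Protocol*

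**What the plan says.** The synopsis gives the end of blinding for those who run the study: "All personnel involved with the conduct of the study will remain blinded until database lock at 12 weeks". The same sentence adds that protocol violations must also have been identified and documented.

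Other passages bear on the same event:

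- **Protocol 9.4.1** covers a different group and names no week: "All personnel involved with the analysis of the study will remain blinded until database lock and protocol violations have been identified and documented".
- **Protocol 6.3** blinds participants, investigators, site staff and sponsor, with no stated end date. It also restricts the analysis code break: "Randomization codes will not be broken for the planned analyses of data until all decisions on the evaluability of the data" have been made and recorded for each participant.
- **SAP 3.1** places the lock after follow-up: "The final clinical lock for writing the CSR will occur once all subjects have completed their full study participation or withdrawn from study".
- **Protocol 9.5 and SAP 5** state that an interim analysis is not applicable.

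The synopsis timeline is "A total treatment period of 12 weeks" followed by "A safety follow-up period of 4 weeks". Protocol 8.3.1 says: "Adverse events will be collected from time of first dose throughout the treatment period and including the follow-up period".

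**The concern.** No other passage mentions a 12-week lock, and the SAP's lock falls later. The end of the blind for conduct staff therefore has two possible dates. Someone who follows the synopsis alone could release codes to conduct staff once Week 12 data are locked, while some participants have not yet reached Visit 9.

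The data still being collected then rest partly on judgement. The investigator answers a yes/no causality question for each adverse event (Protocol 8.3.3). Skin reactions, one of the two categories of special interest, are classified by morphology and graded by the investigator (8.3.6.1). These data enter the treatment comparison. The last dose is scheduled at Visit 8, the SAP's on-treatment period extends 14 days beyond the last dose, and its on-study period runs to the last visit (SAP 3.3.1.2 and 4.6). Both sets of safety tables therefore use data from after Week 12.

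Other rules depend on the same event. The bioanalytical laboratory withholds treatment codes until the study blind is broken (6.3), drug concentrations are withheld until unblinding (8.5.2), and the SAP must be final before database lock (9.4).

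**Working it through.** **Inputs.** Screening of up to 8 weeks, treatment of 12 weeks and follow-up of 4 weeks (Protocol 1.1); Visit 8 on Day 85 and Visit 9 on Day 113 (Table 2); 90 randomized (Protocol 9.2: 45 per arm). The documents give no accrual period, so this is varied.

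**1. The plan's own timeline.** 8 + 12 + 4 = 24 weeks, which agrees with "The study will comprise 3 periods totaling approximately 24 weeks". With Day = 1 + 7 × week, Week 12 is 1 + 84 = Day 85 and Week 16 is 1 + 112 = Day 113. Both match Table 2.

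**2. Gap between the two lock rules.** Synopsis read literally: 113 − 85 = 28 days of scheduled follow-up can fall after the lock. SAP 3.1: 0 days.

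**3. Participants exposed on the literal reading.** Suppose the lock falls on the day the last participant reaches Week 12. Those still in follow-up are the participants randomized in the last 28 days of recruitment. With uniform accrual over M months and no withdrawals:

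number = 90 × 28 / (M × 30.4375)

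Each has on average 28 / 2 = 14 days of follow-up left. Scheduled on-study time for all participants is 90 × 112 = 10,080 participant-days.

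| Accrual (assumed) | Still in follow-up | Share of 90 | Participant-days after lock | Share of 10,080 |
|---|---|---|---|---|
| 6 months | 13.8 | 15.3% | 193 | 1.9% |
| 12 months | 6.9 | 7.7% | 97 | 1.0% |
| 18 months | 4.6 | 5.1% | 64 | 0.6% |
| 24 months | 3.4 | 3.8% | 48 | 0.5% |

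These are upper figures for each accrual length. If the lock comes c days after the last Week 12 visit, the count scales by (28 − c)/28: a 14-day cleaning interval halves it, and one of 28 days or more brings it to zero.

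**4. Do other passages remove the conflict?**

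- Protocol 9.4.1 concerns analysis personnel only, so it does not replace the synopsis rule for conduct personnel.
- The code-break condition in 6.3 turns on evaluability decisions and does not mention Visit 9 or the end of follow-up. Those decisions could in principle be complete at a Week 12 lock.
- SAP 3.1 defines the final lock for the study report. It does not say that there is no earlier lock.
- SAP 4.1.1.1 counts a participant as having completed the study at the end-of-treatment visit or later, whereas Protocol 4.4 requires all phases including the last visit. A lock defined only by study completion would therefore still be ambiguous; Visit 9 should be named.

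**The case against.** The strongest reply is that this is stray wording in a synopsis. The SAP is the later document (April 2024, against March 2023 for the protocol) and is meant to carry the technical detail. It puts the final lock after all follow-up, no interim analysis is planned, and no Week 12 analysis is described. Remaining blinded until a given point sets a minimum and does not order release of codes. Section 6.3 sets no Week 12 end to the blinding of sites, and no passage sends codes to sites while participants are in follow-up. Safety is descriptive and untested, the numbers are small, and rash in healthy volunteers appeared around 7 to 10 days after the first dose (Protocol 4.3), so Weeks 12 to 16 are not the evident risk window.

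Most of this stands, and it limits the point. A reader might infer that late safety data will be collected unblinded, or that ALT results will be released early. The documents do not support either inference: read together they point to one lock after follow-up, with no planned Week 12 readout.

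What the reply does not do is remove the contradiction. The synopsis sentence is current text, it is a stated blinding rule, and it is the only one that dates the end of the blind for conduct staff. A rule that must be corrected by inference from a different document should be reworded.

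**Conclusion.** The synopsis is wrong as written, in a limited sense. It conflicts with SAP 3.1, with the absence of any interim analysis, and with follow-up to Week 16. Literally read, it permits unblinding of conduct staff up to 28 days before a participant's last visit.

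The size is small: about 3 to 14 of 90 participants and roughly 0.5% to 1.9% of scheduled on-study time. This assumes uniform accrual over 24 to 6 months, no withdrawals, a lock on the day of the last Week 12 visit, and codes actually reaching those who rate adverse events. That last step is not shown anywhere in the documents.

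The exposure is confined to adverse event reporting, severity and causality late in follow-up. Week 12 ALT and Pro-C3 samples would already have been taken, so the primary and secondary pharmacodynamic comparisons would not be biased. The documents do not label the follow-up period as blinded; that follows from the double-blind design. The sentence should be corrected, but the point does not call the design into question.

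**What to change.** In the synopsis, replace the reference to a lock at 12 weeks with: *until the final database lock, after the last participant has completed Visit 9 (Week 16) or withdrawn*. Use the same lock definition in Protocol 9.4.1 and apply it there to both conduct and analysis personnel, so that protocol and SAP 3.1 describe one event.

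Keep all existing exceptions in Protocol 6.3: the unblinded data review committee members, the bioanalytical laboratory, emergency unblinding by the investigator, and the sponsor's code break for expedited reporting of serious adverse events. The new sentence should refer to that section and not restate a shorter list.

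The cost is protocol wording only. No sample, visit or analysis changes. If a Week 12 readout was intended, it would come about 4 weeks later.

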## 1.2 Schema

**Figure 1** Study Design

BX, biopsy; NASH, non-alcoholic steatohepatitis; R, randomization

**Table 1** Study Endpoint Assessment

	Screening	R	12-week Treatment Period			FUP
Visit	V1 to V3	V4	V5	V6	V7	V8
Weeks from randomization	Week -8 to -1	Week 0	Week 2	Week 4	Week 8	Week 12
Endpoints		Safety, PK, PD	CC1	CC1	Safety, PK, PD	Safety, PK

An unblinded DRC consisting of AstraZeneca personnel and an external dermatologist will be set up for ongoing, periodic safety monitoring focused on skin reactions and study stopping criteria.  
DRC, data review committee; R, randomization; FUP, follow up; PK, pharmacokinetics; PD, pharmacodynamics; V, visit

### 1.3 Schedule of Activities

**Table 2 Schedule of Activities**

	Screening a						Treatment				Final Follow-up
	Visit 1	Visit 2 b,c	Visit 3	Visit 4	Visit 5	Visit 6	Visit 7	Visit 8/EDV	Visit 9		
Assessment and sampling time points may be adjusted based on emerging data.	Week -8 to -1	Week 0	Week 2	Week 4	Week 8	Week 12	Week 16				
		Day 1	Day 15 ( $\pm 2$ d)	Day 29 ( $\pm 2$ d)	Day 57 ( $\pm 2$ d)	Day 85 ( $\pm 2$ d)	Day 113 ( $\pm 5$ d)				
Informed consent, including consent for genetic testing d	X										
Enrollment in RTSM	X										
Optional informed consent for Genomics Initiative research (Section 8.7, Appendix A)	X										
Inclusion/exclusion criteria (Section 4.4)	X		X								
Liver Biopsy (Section 8.5.1)		X b,c									
Hepatitis B and C and HIV screening (Section 8.2.5) e	X										
Urine pregnancy test (Section 8.2.5) f	X										
COVID-19 tests (Section 8.2.5)	X										
Demographic data	X										
Medical history	X										
Concomitant medication	X	X	X	X	X	X	X	X	X		
Drugs of abuse and alcohol screening (Section 8.2.5)	X										
AUDIT questionnaire (Appendix B)	X										
Randomization					X						

**Table 2 Schedule of Activities**

	Screening a						Treatment				Final Follow-up Visit 9
	Visit 1	Visit 2 b,c	Visit 3	Visit 4	Visit 5	Visit 6	Visit 7	Visit 8/EDV			
	Week -8 to -1		Week 0	Week 2	Week 4	Week 8	Week 12	Week 16			
	Day 1	Day 15 (± 2 d)	Day 29 (± 2 d)	Day 57 (± 2 d)	Day 85 (± 2 d)	Day 113 (± 5 d)					
Assessment and sampling time points may be adjusted based on emerging data.											
Study intervention administration in clinic g											
Study intervention dispensed for at home administration											
Safety and tolerability:											
Collection of AEs and SAEs h	X	X	X	X	X	X	X	X			
BP, pulse rate (supine), and body temperature (Section 8.2.3)	X		X	X	X	X	X	X			
Orthostatic Test (Section 8.2.3.1) i				X			X				
Weight and height (Section 8.2.3)	X (BMI)		X (weight)						X (weight)		
12-lead ECG (Section 8.2.4)	X		X			X			X		
Clinical safety laboratory evaluations, (chemistry, hematology, and urinalysis) (Section 8.2.5) j	X		X k	X	X	X	X	X			
CCI	X					X			X		
Physical examination (Section 8.2.2)	X				X						

**Table 2 Schedule of Activities**

	Screening a						Treatment				Final Follow-up Visit 9
	Visit 1	Visit 2 b,c	Visit 3	Visit 4	Visit 5	Visit 6	Visit 7	Visit 8/EDV			
	Week -8 to -1		Week 0	Week 2	Week 4	Week 8	Week 12	Week 16			
	Day 1	Day 15 (± 2 d)	Day 29 (± 2 d)	Day 57 (± 2 d)	Day 85 (± 2 d)	Day 113 (± 5 d)					
Assessment and sampling time points may be adjusted based on emerging data.											
Brief physical exam (including skin) (Section 8.2.2)			X				X			X	
ANCA testing (Section 8.2.5)		X 									
HbA1c testing (Section 8.2.5)	X										
Blood sample for genetic analysis (Section 8.6.1.1)e				X a							
Pharmacokinetics:											
Plasma for AZD4831 (mituperstat) PK (Section 8.5.2)				X o (predose)			X			X	
Pharmacodynamics:											
Fasting blood, plasma, and urine sampling for biomarkers (Section 8.5.3)		X o (predose)					X			X	
Optional Exploratory Samples:											
Exploratory fasting biomarker sampling (optional) (Section 8.6.2)j			X								
Genomics Initiative optional, exploratory genetic sample (Section 8.7, Appendix A)				X							

a Participants, including participants who are rescreened, can be randomized anytime within the screening period outlined in the SoA once all inclusion criteria have been fulfilled.

b Participants with historical biopsy and meeting all inclusion criteria are not required to have Visit 2. All participants must have Visit 1 and 3 prior to randomization.

- c Visit 2 and the fresh liver biopsy screening are only required if there is no histologically confirmed NASH as diagnosed by liver biopsy within 12 months of provision of written informed consent. For participants without a historical biopsy, the screening liver biopsy will be scheduled after all Visit 1 screening procedures and once it has been confirmed that the participant meets all other inclusion/exclusion criteria and safety laboratory assessments are available.
- d Consent and sample collection for mandatory genetic testing will only be conducted in countries where genetic testing is allowed in this study.
- e If positive for HIV at Visit 1, a reflex test will be performed on the remaining sample. Further confirmation is available with optional HIV RNA test, available in retest kit. If positive for hepatitis C at Visit 1, a hepatitis C RNA test will be triggered to confirm the result.
- f Urine pregnancy test required for WOCBP only. If there is a suspicion of pregnancy, urine pregnancy test should be repeated prior to first dosing.
- g Participants will receive study intervention at the site on Day 1, Day 29, and Day 85 and at home once daily on other days. Study intervention will be administered after PK sampling. At Visit 4 and Visit 6, study intervention will be administered from a newly dispensed bottle. At Visit 8, study intervention will be administered from the previously dispensed bottle (brought from home).
- h AEs will be collected from the time of first dose (the only exception is related to the pre-dose orthostatic test at Visit 4; if orthostatic hypotension is confirmed, it should be reported as an AE, and symptoms related to the measurement of orthostatic vitals if present should also be reported as an AE). SAEs will be collected from signing of ICF.
- i Orthostatic BP will be measured at Visit 4 and at Visit 8 prior to any required blood draw and study intervention and 1-2 hours post dose at Visit 4.
- j Orthostatic BP will be measured 1 and 3 minutes after the participant stands.
- l Blood draws for clinical safety, **CC1** and exploratory fasting biomarker sampling will be drawn pre-dose (where applicable).
- m HbA1c results needed to determine eligibility.
- n If for any reason the sample is not drawn at Visit 4, it may be taken at any visit until the last study visit.
- o In a subset of participants (approximately 20%), 2 additional postdose samples will be collected at Visit 6. Visit 6 sample collection times are: pre-dose, and 0.5 to 1.5 h and 1.5 to 3 h, with a minimum of 1 hour between the postdose sampling occasions. Once approximately 20% of participants have been tested, no further participants would need this additional post dose sampling.

AE, adverse event; ANCA, antineutrophil cytoplasmic antibody; AUDIT, Alcohol Use Disorder Identification Test; BP, blood pressure; COVID-19, coronavirus disease 2019; ECG, electrocardiogram; EDV, early discontinuation visit; HbA1c, hemoglobin A1c; HIV, human immunodeficiency virus; ICF, informed consent form; NASH, non-alcoholic steatohepatitis; PCR, polymerase chain reaction; PK, pharmacokinetic(s); RNA, ribonucleic acid; RTSM, randomization and trial supply management; SAE, serious adverse event; SoA, schedule of activities; **CC1**

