## 5 STUDY POPULATION

Prospective approval of protocol deviations to recruitment and enrollment criteria, also known as protocol waivers or exemptions, is not permitted.

Each participant should meet all the inclusion criteria and none of the exclusion criteria to be assigned/randomized to a study intervention. Under no circumstances can there be exceptions to this rule. Participants who do not meet the entry requirements are screen failures (Section 5.4).

In this protocol, “enrolled” participants are defined as those who sign informed consent. “Randomized” participants are defined as those who undergo randomization and receive a randomization number.

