### **Reproduction**

- 7 Male and/or female. Contraceptive use by women should be consistent with local regulations regarding the methods of contraception for those participating in clinical studies.
  - (a) Criterion not applicable to this CSP version.
  - (b) Criterion not applicable to this CSP version.
  - (c) Female participants:
    - Female participants must not be pregnant or lactating.
    - Females of childbearing potential who are sexually active with a non-sterilized male partner must agree to use an acceptable method of birth control, from enrolment throughout the study and until at least 4 weeks after last dose of study intervention. Acceptable methods of contraception include birth control pills, injections, implants or patches, intrauterine devices, and tubal ligation/occlusion. The following are not acceptable methods of contraception: periodic abstinence (calendar, symptothermal, post-ovulation methods), withdrawal (coitus interruptus), spermicides only, and lactational amenorrhoea. Female condom and male condom should not be used together.

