#### **6.4 Study Intervention Compliance**

Study intervention will be administered in clinic on the day of randomization (Day 1, Visit 4), Day 29 (Visit 6), and Day 85 (Visit 8). Participants will self-administer study intervention at home on other days.

At Visit 8, a new bottle will not be dispensed at the site, and the participant will receive study intervention from the bottle they have brought from home. When participants are dosed at the site, they will receive study intervention directly from the investigator or designee, under medical supervision, after checking treatment was not taken at home before coming to the study site. The date, and time if applicable, of dose administered in the clinic will be recorded in the source documents and recorded in the eCRF. The dose of study intervention and study participant identification will be confirmed at the time of dosing by a member of the study site staff other than the person administering the study intervention.

When participants self-administer study intervention at home, compliance with study intervention will be assessed at each visit. Compliance will be assessed by direct questioning and counting returned tablets during the site visits and documented in the source documents and eCRF. Deviation(s) from the prescribed dosage regimen should be recorded in the eCRF. Participants will be provided with a dosing card to record the dose intake information (date and time) for each dose.

A record of the number of AZD4831 (mitiperstat)/placebo tablets dispensed to and taken by each participant must be maintained and reconciled with study intervention and compliance records. Intervention start and stop dates, including dates for intervention delays will also be recorded in the eCRF.

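### The only scheduled pregnancy test can precede the first dose by up to 56 days, so an unsuspected conception during screening would not be detected before dosing

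*Protocol*

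**What the plan says.** Table 2 of the protocol (Section 1.3) gives the urine pregnancy test its own row, marked once, at Visit 1. The amendment summary also places the row at that visit. Footnote f sets the rule: "Urine pregnancy test required for WOCBP only. If there is a suspicion of pregnancy, urine pregnancy test should be repeated prior to first dosing".

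The synopsis allows "A screening period of up to 8 weeks", and the amendment summary expresses this as 56 days. Some participants wait less: "For participants who have a historical biopsy and elevated alanine aminotransferase (ALT), the screening period can be shortened". Section 6.4 puts the first dose in the clinic on the day of randomization, which is Day 1 at Visit 4.

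On eligibility, criterion 7(c) states "Female participants must not be pregnant or lactating". The same criterion sets a contraception rule for women who could conceive with their partner: "must agree to use an acceptable method of birth control, from enrolment throughout the study and until at least 4 weeks after last dose". Section 5 adds: "Each participant should meet all the inclusion criteria and none of the exclusion criteria to be assigned/randomized to a study intervention".

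**The concern.** Eligibility has to hold at randomization, but the evidence on pregnancy can be eight weeks old by then. A woman who conceives after Visit 1 and does not suspect it would meet no scheduled test before dosing. She could be randomized and treated although criterion 7(c) excludes her.

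Other criteria that can change are checked on the day. Blood pressure (criterion 30) can exclude at screening or at randomization, and heart rate (criterion 31) is assessed at randomization. Pregnancy status is not retested.

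Two changes in Amendment 1 combine here. It admitted women of childbearing potential, and it lengthened screening from 42 to 56 days. What is at stake is avoidable fetal exposure to an investigational drug. The size of that hazard cannot be judged from the visible text.

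**Working it through.** **Longest gap between test and first dose**

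- Only scheduled test: Visit 1 (Table 2).
- First dose: Visit 4, Day 1 (Section 6.4).
- Maximum screening: 8 weeks (synopsis). 8 × 7 = 56 days, which matches the amendment summary. The study total also agrees: 8 + 12 + 4 = 24 weeks.
- Scheduled tests after Visit 1 and before first dose: none.

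The figure of 56 days is a maximum. Participants may be randomized at any point in the window once eligible. Rescreened participants repeat the enrolment procedures (Section 5.4), and so repeat the test.

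**Could a later test be implied elsewhere?**

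Table 7 lists a pregnancy test among the urine safety variables, and Table 2 schedules urinalysis at Visit 4. Three points argue against reading a Visit 4 pregnancy test into this:

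1. Section 8.2.5 takes visit timing from Table 2, where the test has a separate row marked only at Visit 1.
2. HbA1c is treated in the same way: it is listed in Table 7 and has its own Visit 1 row in Table 2.
3. A repeat on suspicion before first dosing would be largely redundant if every woman were tested at Visit 4 anyway.

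**Size**

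The documents give neither the number of women of childbearing potential nor a conception rate. Both ranges below are assumptions.

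- Women of childbearing potential, 10% to 30% of 90: 0.10 × 90 = 9 to 0.30 × 90 = 27. At 1:1 allocation, 4.5 to 13.5 receive drug.
- Conception rate under the required contraception: 0.01 to 0.10 per woman-year.
- Expected conceptions in the gap = women × rate × 56/365.
  - Low: 9 × 0.01 × 56/365 = 0.014.
  - High: 27 × 0.10 × 56/365 = 0.41.
- Active arm, half of these: 0.007 to 0.21.

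Under these assumptions the results are upper bounds on what a Visit 4 test would prevent. Every woman is given the full 56 days. No deduction is made for pregnancies that are suspected and so retested, or for conceptions too recent for a urine test to show.

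**Effect of a Visit 4 test**

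The longest gap from the last scheduled test to first dose falls from 56 days to 0.

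**The case against.** The strongest reply is that the sponsor considered this risk and layered its protections: contraception from enrolment, a test at entry, a repeat on suspicion, and immediate discontinuation if pregnancy occurs (Section 8.3.9.1). Amendment 1 classed these changes as substantial. Eligibility is also reviewed again at Visit 3, which every participant must attend, and that review could raise a suspicion and so trigger the repeat. Whether one test is enough depends on reproductive-toxicity information that is not in these documents, and the event is rare on any reasonable assumption.

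Much of this is fair and limits the weight of the point. It does not close the gap. Contraception reduces conceptions but does not reveal one. The Visit 3 review brings no new pregnancy result, so it cannot detect a pregnancy that nobody suspects. Discontinuation acts only after exposure. Table 7 leaves some ambiguity that the sponsor could clear up, but the reading that favours a Visit 4 test is the weaker one.

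Two limits of scope also stand. The SAP introduction refers to three regional protocols, and this point concerns only the version supplied. In addition, no test is scheduled during treatment. On the same upper assumptions, the 12 weeks of dosing would carry 13.5 × 0.10 × 84/365 = 0.31 active-arm conceptions, against 0.21 in screening. A Visit 4 test does not address that period.

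**Conclusion.** The concern holds for the protocol dated 20 March 2023. The plan as written permits randomization and dosing of a woman whom its own criteria exclude, because the only scheduled pregnancy test may be up to 56 days old. That conclusion rests on the text alone. The estimate of 0.01 to 0.41 conceptions (0.007 to 0.21 in the active arm) rests on assumed inputs and should be read as an upper bound. The likelihood is low and the primary analysis is unaffected, but the exposure could be serious and is cheap to guard against. The change is worth making.

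**What to change.** Add a mark at Visit 4 in the existing urine pregnancy test row of Table 2, and reword footnote f along these lines: *WOCBP only: urine test at Visit 1 and again at Visit 4. A negative Visit 4 result, read on site, is required before randomization and first dose.* Keep the provision for repeating the test on suspicion, and keep the contraception requirement, since a urine test cannot show a very recent conception.

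Urine is already scheduled at Visit 4 for urinalysis. Section 8.2.5 sends urinalysis to a central laboratory, however, so the strip must be read at the site, and the urine must be collected before randomization.

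The cost is one strip and a short on-site step per woman of childbearing potential, plus one table mark and a footnote edit. Amendment 1 classed the addition of footnote f as substantial, so ethics and regulatory approval would be needed. The downside is a rare screen failure on the day of randomization, which criteria 30 and 31 can already cause.
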